9.9 Limitations of the Research Methods

9.9.1 Limitations of Registry Data Collection

The transplant registries used for this study have definite strengths for the collection of real-world data, particularly for those outcomes that are transplant-specific such as neutrophil recovery and secondary malignancy development. While registry data to be collected for this study is very broad, it may not be as granular as clinical trial data. This is an expected limitation of observational, real-world studies. Where feasible, additional data collection is being integrated in consultation with the registry personnel, balancing appropriate level of detail in the data collection to meet the study objectives with the burden of time placed on transplant personnel and their ultimate willingness to participate in the study.

For example, it is deemed by the registries that collection of the laboratory results most proximal to the patient's data reporting period (e.g., 6 months, 1 year) is sufficient to identify any long-term abnormalities and allows to limit the burden of data entry placed on the transplant center personnel. While longitudinal laboratory results will only be collected at pre-specified timepoints, it is unlikely that safety events will be missed due to this limitation because a broad range of hard endpoints (i.e., disease diagnoses) are included in this study and uploaded into the registry by transplant center personnel.

In a similar manner, registries will collect comprehensive data on number of severe VOC events among patients with SCD in each reporting interval and time from HSCT to most recent severe VOC event but will not capture the date of each possible severe VOC event over the 15-year study duration. This approach was deemed to be optimal, allowing the capture of information necessary to meet the study objectives without limiting the feasibility of the study by the undue burden of data collection on the participating transplant centers.

Of note, study analyses will be based on a combination of both standard, routinely collected registry data (secondary data) and de-novo data collected specifically for the study (primary data). Primary versus secondary data availability will vary by registry, due to different regional collection practices. All de novo study questions will be designed with the aid of registry personnel, in combination with transplant center personnel, to ensure question comprehensibility and data availability. As with the standard registry questions, de novo questions will be accessed

through the registry platform and subject to CIBMTR and EBMT quality control standards as described in the study data management plan.

9.9.2 Potential Confounding Factors

Though patients receiving an allogeneic transplant for SCD or TDT are generally expected to be of similar disease severity and undergo similarly rigorous conditioning regimens as patients receiving exa-cel, the final characteristics of the Allo-HSCT Cohorts may differ from the Exa-cel Cohorts. Confounding factors in the SCD and TDT literature affecting the major safety outcomes include increased age at transplant (neutrophil recovery / graft failure, mortality), allogeneic donor source (neutrophil recovery / graft failure, mortality), allogeneic stem cell source (neutrophil and platelet recovery) and conditioning regimen (malignancy development). Additional factors affecting the safety outcomes relevant to individuals with SCD or TDT may include impaired splenic function (neutrophil and platelet recovery), baseline iron overload (platelet recovery, malignancy development), and infused cell dose (neutrophil and platelet recovery). The potential confounding factors for each of the key safety outcomes are discussed in more detail below:

- Neutrophil engraftment failure: Both increased age (e.g., >15 years) at time of transplant¹⁸ and mismatched allogeneic donor type have been identified as risk factors to graft failure in SCD and TDT populations.^{19, 20} Relevant factors from the general transplant outcomes literature include splenic enlargement^{21, 22} and infused cell dose.^{23, 24}
- **Platelet recovery**: Risk factors for delayed platelet recovery are not well studied in SCD and TDT populations, but include cord blood transplant^{25, 26} and, relevant from the more general HSCT literature, splenic enlargement^{21, 22}, pre-transplant iron overload^{27, 28}, pre-transplant transfusion dependence²⁴, and infused cell dose.^{23, 24}
- **Post-allogeneic transplant malignancy**: The literature has reported primarily hematologic malignancy development among patients receiving transplants for SCD²⁹ and solid tumor development among patients receiving transplants for TDT.^{30, 31} Risk factors for malignancy development among allo-HSCT treated patients with SCD include graft failure and/or receipt of low-intensity non-myeloablative conditioning regimens²⁹; these factors are presumed to be applicable to patients receiving transplants for TDT. Treated patients with TDT may also be at risk of malignancy due to chronic iron exposure to the major organs / tissues.³²
- **Post-transplant mortality**: Transplant-related factors associated with increased risk of mortality include older age (e.g., >15 years) at transplant and transplants from mismatched donor sources.^{18-20, 25}

Subgroup comparison (stratification) will be the primary analytical method used to adjust for factors (confounders) known or suspected to be associated with post-transplant outcomes. Subgroup analyses pre-specified in the protocol include: (i) age group at transplant, (ii) patient genotype, and (iii) country of transplant (if sufficient patient counts to preserve anonymity), but may also include allogeneic stem cell source (cord blood, bone marrow, peripheral blood), level of donor matching in the Allo-HSCT comparator(human leukocyte antigen [HLA]-matched related or unrelated, HLA-mismatched, haploidentical) or conditioning regimen (e.g., fully myeloablative, reduced intensity, non-myeloablative) after assessment of the enrolled cohort differences. Additional ad hoc statistical analyses may be implemented, as needed – this may include modeling to adjust for differences in cohort characteristics in between-cohort analyses

and/or time to event analyses for select outcomes. Subgroup analyses, split by these potential confounding factors, may be performed on a post-hoc basis to control for unexpected differences between the final enrolled comparator and exa-cel treated cohorts, unexplained differences in outcomes or other findings that require exploration.

9.9.3 Sample Size Limitations

Small sample sizes are a known challenge inherent in working with rare disease populations.³³ Exa-cel therapy, indicated for individuals with the most severe phenotypes within known rare disease populations, is expected to only be available to relatively small numbers of individuals. Smaller sample sizes may limit identification of uncommon safety signals or prevent powerful analytic comparisons. In addition, given the smaller sample size, some subgroup analyses may not produce informative results. To maximize the data collection and inferential ability within this study, a broad range of hard endpoints (i.e., disease diagnoses) and early indicator (i.e., laboratory value) variables are included in this study; these variables, in combination with data on disease-related symptoms and therapies, will aid in characterizing the safety and durability of exa-cel effects. Moreover, data collection will occur at least annually, allowing repeated measures of patient outcomes over time.

9.9.4 Missing Data

Due to the observational nature of this study, some patients may have missing visits and/or missing data. Data may be missing from either the pre-treatment or post-treatment periods. The registries included in this study incorporate robust systems to minimize missing data. As described in Section 9.8, participating centers will be incentivized and monitoring procedures and source data verification will be put in place to maximize the data quality and completeness. All efforts will be made to ensure that the level of missing data for key variables of interest does not exceed 20% (considered acceptable to support regulatory decision-making based on the published literature).³⁴

The study progress reports will include statistics on the percent missing data for the key variables of interest.

Although no imputation of missing data will be conducted in the course of statistical analyses, if data are missing for more than 20% of the patients, additional analyses may be performed to understand if there are any systematic differences between patients with and without missing data to assess the direction and magnitude of potential bias.

9.9.5 Loss to Follow-Up

Due to the targeted 15-year duration of follow-up, patients may be lost to follow-up over time. This may occur as adult and pediatric patients change their resident city, state, or country over time. Importantly, this loss to follow-up may be differential as patients experiencing the best post-transplant outcomes may reduce contact with their care providers. All efforts will be made to minimize losses to follow-up among the study participants, regardless of transplant type received or transplant outcome.

Measures to ensure long-term follow-up will include a combination of both transplant center and patient-specific interventions. In addition to standard patient-tracking routines, transplant centers participating in this sponsored study may receive additional education, patient tracking support, and/or tracking incentives based on annual patient follow-up. Patients, at the time of treatment

and/or initial consent / assent, will receive education on the importance of long-term follow-up contacts and, with additional consent / assent, may receive patient-friendly study updates.

The study progress reports and interim analysis reports will include statistics on the potential loss to follow-up for each study cohort. Analyses will be performed to understand if there are any systematic differences between patients lost to follow-up and remaining in the study to assess the direction and magnitude of potential bias.

9.9.6 Study Generalizability

This is a study conducted in a real-world setting using primary and secondary data collected from the EBMT and CIBMTR patient registries. Though the registries provide robust coverage across their target regions, the availability of exa-cel in the commercial setting will be limited to: (i) countries where regulatory and reimbursement approvals are achieved and (ii) select treatment centers with physicians experienced in HSCT and treatment of patients with β -hemoglobinopathies. As such, exa-cel may only be available to a limited number of indicated patients globally - this study will further include only a subset of those patients, which warrants a discussion of study generalizability to the broader population of patients who might be eligible for exa-cel. Two factors, the indicated diseases presentation and exa-cel mechanism of action, suggest that the findings from this study will be generalizable to the global indicated population:

• Indicated diseases presentation

- TDT Patient Population: β-thalassemia is a rare, autosomal recessive disorder that is highly linked to ethnicity and is often associated with individuals originating from the Mediterranean, the Middle East, South Asia, and Southeast Asia. Transfusion dependence occurs in all ethnicities and regions and is the same irrespective of ethnicity or region.³⁵
- SCD Patient Population: SCD is a rare, autosomal recessive disorder that is highly linked to ethnicity. Globally, including in the US, SCD occurs at disproportionately high rates among individuals of African descent and, to a lesser extent, among individuals of Middle Eastern, Mediterranean, Indian, and Asian descent.^{36, 37} Severe VOCs requiring a medical visit occur in all ethnicities and regions and are the same irrespective of ethnicity or region.³⁸
- **Mechanism of action**: The nature of the exa-cel drug product, an autologous gene-edited cellular therapy, is such that it is "ethnically insensitive" (based on Regulatory Guidance ICH E5 [R1])³⁹; with no differences in efficacy or safety related to difference in pharmacokinetics or pharmacodynamics anticipated based on the mechanism of action. Furthermore, there was no difference in safety or efficacy identified based on geographic location of subjects that were dosed with exa-cel in the clinical program.

Furthermore, as discussed previously in Section 9.2, international and regional guidelines suggest that the standard of care for patients with SCD and TDT is similar across regions.¹⁻⁴ In summary, results from this study are expected to be generalizable to patients treated with exa-cel in Europe and US, and more broadly, across all regions where exa-cel is expected to be available.

10 PROTECTION OF HUMAN SUBJECTS

10.1 Subject Information and Informed Consent

Informed consent and/or informed assent will be collected for all study participants. The patient or patient's guardian (if the patient is a minor) will be provided with appropriate forms at the transplant centers prior to any data collection. Patients who are minors at the time of assent may be requested to re-confirm their individual consent / assent when they reach the age of majority, as specified by country.

10.1.1 EBMT

Following the General Data Protection Regulation (GDPR), and to ensure the maximum accordance with the law in all EU / European Economic Area nations, personal data of patients residing in EU member countries shall only be used for research through the EBMT when appropriate informed consent is ensured. This has been common practice for many years. The informed consent is collected by the individual centers or donor registries submitting data to the EBMT to make certain that the respective national laws are followed. The EBMT makes patient consent a prerequisite for submitting the data and provides all necessary information about usage of the data, to ensure appropriate consent is obtained in all cases. Post-authorization study informed consent form templates are provided to all countries. Copies have been / will be submitted to Competent Authorities and ethics committees where applicable for approval.

10.1.2 CIBMTR

Data are collected, stored and shared under terms of the *Protocol for a Research Database for Hematopoietic Cell Transplantation, Other Cellular Therapies and Marrow Toxic Injuries* and its accompanying consent forms.⁴⁰ To be compliant with US federal regulations for human research subject protection, all US centers are required to have a Federal Wide Assurance with the Office for Human Research Protection and, as part of their Data Transmission Agreement with the CIBMTR, agree to obtain local IRB approval for the CIBMTR Research Database Protocol (http://www.ClinicalTrials.gov; Identifier: NCT01166009). The National Marrow Donor Program IRB serves as the IRB of record for all research conducted by the CIBMTR. The center is responsible for obtaining the necessary institutional review and recipient consent for participation in the CIBMTR Research Database and submitting the documents to the CIBMTR Protocol Coordinator.

If the recipient does not consent to participate according to the respective country's laws and regulations, the CIBMTR requests that only the Pre-TED and Pre-TED Disease Classification be submitted. This information helps ensure the epidemiological integrity of the Research Database is maintained and does not require provision of any protected health information that could identify the recipient, nor is this information used in any analysis.

The CIBMTR works within the NMDP / Be The Match maintained comprehensive Human Research Protection Program to ensure the rights and welfare of participants in its research are protected and to ensure compliance with all pertinent US federal regulations. The NMDP / Be The Match Human Research Protection Program is fully accredited by the Association for the Accreditation of Human Research Protection Programs.

10.2 Access to Records

The study sponsor will not have access to patient records.

10.3 Subject Privacy

10.3.1 EBMT

All personal data under the responsibility of the EBMT are processed according to the EU GDPR. The data are stored in an Amazon Web Services environment with infrastructures located in Europe (EU-west-1, EU-west1a, and EU-west-1b) which is protected by safeguards that ensure security, including compliance with ISO27001 certification. The data are only accessible by EBMT employees for the performance of their job following a stringent access control policy. The EBMT has Privacy Policies, a Register of Processing Activities, and data use and processing policies in place.

EBMT has developed a Joint Controllership agreement with centers with full EBMT membership which describes the responsibilities concerning data protection of the data reported to the EBMT.

10.3.2 CIBMTR

The CIBMTR protects the data and information received from centers and patients and is committed to the ethical conduct of research. CIBMTR obeys the US Health Insurance Portability and Accountability Act (HIPAA) and the EU GDPR.

The CIBMTR maintains comprehensive information security and data protection practices that align with the National Institute of Technology and Standards (NIST 800-53) Security and Privacy Control for Federal Systems framework as well as the policies and procedures of the CIBMTR and its parent institutions. These practices are continuously monitored and subject to annual assessment by a qualified, independent third-party auditor. Assessment findings and a statement of fact are reported to the CIBMTR Information Security and Data Protection Committee for acceptance and, upon request, are made available as part of a security assurance package to key stakeholders.

When releasing data, the CIBMTR is obligated to ensure that datasets do not contain protected health information. CIBMTR staff follow a standard procedure for creation of de-identified datasets that specifies removal of all patient, donor, and center identifiers, which could lead to the identification of a patient or center from data files. The CIBMTR does not release to the principal investigator or any other member of his / her research team identifiable patient or center variables unless these data are critical to the approved study / project or will be used for linking to another data file via an established honest broker relationship. In these cases, special procedures outlined in the CIBMTR Linking Data to External Databases or Data Sources Standard Operating Procedures are followed and documented with a Data Use Agreement and established prior to final approval of the request.

11 MANAGEMENT AND REPORTING OF ADVERSE EVENTS / ADVERSE REACTIONS

The reporting procedures defined below by this non-interventional study protocol are applicable to study patients exposed to exa-cel accessed via commercial availability.

In addition to the reporting procedures defined in this protocol, the HCP is responsible for reporting safety information to regulatory authorities, ethics committees, and other local agencies, in accordance with local regulatory requirements, as applicable.

11.1 Definitions

• Adverse Event

An AE is defined as any untoward medical occurrence in a subject during the study; the event does not necessarily have a causal relationship with the treatment. This includes any newly occurring event or previous condition that has increased in severity or frequency. A subset of AEs may meet serious criteria.

Planned hospital admissions or surgical procedures for an illness or disease that existed before the subject was screened in the study are not to be considered AEs unless the condition deteriorated in an unexpected manner during the study (e.g., surgery was performed earlier than planned).

• Serious Adverse Event

An SAE is any AE that meets any of the following criteria:

- Results in death
- Life-threatening
- Requires hospitalization or prolongation of existing hospitalization
- Results in persistent or significant disability / incapacity (substantial disruption of the ability to conduct normal life functions)
- Congenital anomaly or birth defect
- Important medical event that, based upon appropriate medical judgment, may jeopardize the subject or may require medical or surgical intervention to prevent 1 of the outcomes listed above (e.g., a new hematologic malignancy diagnosis).

11.2 Adverse Event Causality

Every effort should be made by the HCP to assess the relationship of the AE, if any, to exa-cel exposure. Causality should be classified using the categories presented in Table 3.

Classification	Definition
Related	There is a suspected association between the event and exa-cel, a plausible mechanism for the event to be related to exa-cel and causes other than the exa-cel have been ruled out.
Not Related	The event is believed related to an etiology other than the exa-cel.
1 1	1

Table 3Classifications for Adverse Event Causality

exa-cel: exagamglogene autotemcel

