9.7.5 Other Analyses

Additional key outcomes will also be evaluated for each cohort from each registry for each time point of the post-transplant period. Findings will be summarized as categorical or continuous measures, as appropriate:

• Post-transplant complications

- Post-transplant health status measures
- Post-transplant disease-related therapies
- Post-transplant additional laboratory measures, including relevant CBC results at each available timepoint throughout the study duration
- Post-transplant pregnancies

In addition to all analyses of the pre-specified outcome variables (Section 9.3.3 through 9.3.5) for both the exa-cel and allogeneic HSCT cohorts, Serious Adverse Events (SAEs) among participating exa-cel recipients reported to the sponsor per Section 11 will be provided with each study report as a summary tabulation (proportion of exa-cel treated patients with SAE reports, by type) and in a listing format. Findings from the hematologic malignancy evaluation (Section 12) will also be provided, where available.

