11.3 SAE Reporting Procedure

All SAEs observed in patients exposed to exa-cel accessed via commercial availability, regardless of the presumed relationship to any Vertex medication exposure, must be reported to

the MAH using the Non-interventional (NI) Study Safety Information Collection Form (study number must be included on the form).

Any hematologic malignancy diagnosis is considered an important medical event that must be reported to the MAH following SAE reporting guidance.

This reporting is required from the time informed consent and assent, where applicable, is signed and while the patient is participating in the study, for all SAEs that occur at any time after exa-cel infusion. Complete and comprehensive case information must be documented and causality assessments performed.

Reportable SAEs should be reported by the HCP to the MAH **within 24 hours** of awareness. NI Study Safety Information Collection Forms should be submitted to:

Vertex Global Patient Safety

Email: [contact] (*preferred*) Or via [contact] For questions, contact [contact]

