11.4 Pregnancy Reporting

If a female patient or female partner of a male patient becomes pregnant while being treated with exa-cel, the HCP must notify the MAH (Vertex Global Patient Safety) of the pregnancy using the Pregnancy Information Collection Form. The patient will be followed until the end of the pregnancy, and the infant will be followed for 1 year after the birth, provided informed consent is obtained. A separate informed consent form will be provided to explain these follow-up activities.

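### Table 3 makes Related depend on excluding every other cause and leaves indeterminate events without a class; Section 11.4's pregnancy trigger has no workable meaning for a single infusion

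*Protocol*

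**What the plan says.** **Causality.** Section 11.2 asks the treating HCP to rate the relationship of each event to exa-cel with the classes in Table 3. Related needs three things together: a suspected association, "a plausible mechanism for the event to be related to exa-cel and causes other than the exa-cel have been ruled out". The entry for Not Related reads "The event is believed related to an etiology other than the exa-cel". Section 11.3 requires a causality assessment for the SAEs that are reported.

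**Competing causes.** Section 9.9.2 expects allo-HSCT and exa-cel patients to be conditioned with similar rigor. Its list of factors affecting the main safety outcomes includes "and conditioning regimen (malignancy development"). It also names baseline iron overload for malignancy and platelet recovery, and impaired splenic function for neutrophil and platelet recovery.

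**Pregnancy.** Under Section 11.4, if a patient or a male patient's partner "becomes pregnant while being treated with exa-cel, the HCP must notify the MAH". That section also sets the follow-up of the pregnancy to its end and of the infant for one year, subject to consent.

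**The concern.** Table 3 asks the physician to exclude everything else before suspecting the product. In this population other explanations are built into the treatment: every exa-cel patient is conditioned, and many may carry iron overload. A physician who suspects exa-cel but cannot exclude conditioning has no correct class to choose. If such events go by default to Not Related, the ratings lean toward no signal because of the definition and not because of the evidence. Primary objective 1 is the long-term safety of exa-cel. Outside hematologic malignancy, the Table 3 rating is the only causality assessment that the protocol specifies.

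The pregnancy rule has a similar fault. A trigger worded for ongoing treatment is applied to a product infused on one day. Read literally, it covers almost none of the follow-up in which pregnancies will occur, and the infant follow-up hangs on it.

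**Working it through.** The protocol states no figure on this point, so the check sets its sections side by side.

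**1. Do the two classes cover all events?** Take an event where the physician suspects exa-cel and sees a plausible mechanism.
- Other causes excluded: Related.
- Another cause believed responsible: Not Related.
- Another cause neither excluded nor believed responsible: no class applies.

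The third case is the ordinary one when a known competing factor is present.

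**2. How often is a competing factor present?** For malignancy, conditioning is a named factor, and Section 9.1 treats it as part of the peri-transplant period for every included patient. Iron overload is a second named factor. For delayed platelet recovery, Section 9.9.2 names iron overload and splenic function, and for neutrophil recovery splenic function; it does not name conditioning for either. The support is therefore strongest for malignancy and weaker for cytopenia.

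**3. Does Table 3 agree with Section 12?** Section 12 has the MAH examine whether genome editing may have had a part in each confirmed hematologic malignancy, and weighs how far pre-existing genomic drivers contributed. That is a contributory question. Table 3 sets an exclusive one. The same case could fail the Related test under Section 11.2 and still be found under Section 12 to involve editing.

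**4. Does the rating decide what is captured or analyzed?**
- Section 11.3: SAEs in exa-cel patients, "regardless of the presumed relationship to any Vertex medication exposure, must be reported to" the MAH.
- The same section applies this "for all SAEs that occur at any time after exa-cel infusion", while the patient is in the study.
- Also Section 11.3: "Any hematologic malignancy diagnosis is considered an important medical event that must be reported to the MAH following SAE reporting guidance".
- Section 9.7.5: SAEs go into each report as a "summary tabulation (proportion of exa-cel treated patients with SAE reports, by type) and in a listing format", with no filter on relatedness.
- Sections 9.3.3 and 9.7.3: neutrophil and platelet recovery, new malignancy, hematologic disorder and mortality carry no causality rating.
- Section 12: the malignancy work-up is triggered by the confirmed diagnosis.

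So it does not. Only the rating itself is affected.

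**5. What is the pregnancy window?** Section 9.7.1 defines Day 0 as the day of infusion, so a literal treatment period is one day. Table 2 collects pregnancy and outcome at Day 100, Month 6, Year 1 and annually in Years 2 to 15, which is 3 + 14 = 17 scheduled points. Section 9.3.5 covers patient or partner and, for live births and where available, growth-related findings. Section 9.7.5 summarizes post-transplant pregnancies. The registries therefore record pregnancies to Year 15, but MAH notification and the one-year infant follow-up stand only in Section 11.4. SAE reporting may not close that gap: Section 11.1 defines an AE as occurring in a subject, and a partner or infant is not clearly one, although congenital anomaly is listed as a seriousness criterion.

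**The case against.** The strongest reply is that nothing the study reports as a safety result turns on Table 3. SAEs are reported and tabulated whatever the rating, hematologic malignancies are investigated on diagnosis, and the primary outcomes come from the registries. The protocol plans no analysis of causality ratings. All of this stands. A reader might infer that exa-cel signals would be lost, or that the sponsor's view of off-target risk would be biased; steps 3 and 4 of the working show that the documents do not support either.

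A reader might also infer that Related is impossible, or that its attainable rate is near zero. That goes too far. The Section 12 work-up gathers evidence that could exclude some alternatives, and the detailed malignancy evidence in Section 9.9.2 concerns allo-HSCT, graft failure and low-intensity regimens. Only the summary sentence names conditioning generally. That indeterminate events will be filed as Not Related is likewise an expectation; the collection form is not shown.

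On agreement with Section 12, one can reply that Section 9.1 describes the same work-up in more strictly causal terms. But Section 12 governs the investigation, and its question is contributory.

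On pregnancy, one can say that a reading confined to the infusion would leave Section 11.4 nearly empty, so sites would read it more broadly. That is plausible, but then each site sets its own window. A reader might infer a 15-year loss of pregnancy data; registry collection rules that out.

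**Conclusion.** The point holds, within limits, for two separate rules.

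- **Table 3** sets an exclusive test for Related and leaves a gap between its two classes. Followed literally, it under-classifies relatedness in physicians' ratings, most clearly for malignancy. The conclusion that Related will rarely be attainable is an inference from the factors the protocol names. It assumes that a physician can seldom exclude conditioning or iron overload in an individual case. It also assumes that Table 3 has only the two classes shown; a third class would close the gap but would not loosen the test for Related.
- **Section 11.4** has no workable window for a single infusion. It matches neither the post-infusion window of Section 11.3 nor the collection to Year 15 in Table 2. Later pregnancies could miss MAH notification and the infant follow-up, while still being recorded by the registries.

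No rate can be put on either effect from the protocol. The Table 3 rule applies to every reported SAE among the planned minimum of 100 + 100 = 200 exa-cel patients. The point is modest in weight but worth correcting, since both rules are fixed in the protocol itself and are not matters left to an SAP.

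**What to change.** In Table 3, define Related as a reasonable possibility that exa-cel caused or contributed to the event, stating that other possible causes need not be excluded. Define Not Related as no reasonable possibility. The two classes then cover all events and agree with the question asked in Section 12.

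In Section 11.4, reconcile the trigger with Section 11.3 and Table 2, so that notification applies to pregnancies arising at any point after infusion while the patient is in the study.

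The cost is about two sentences and an update of the collection forms. More SAEs will be rated related, and because many transplant events have several possible causes, the rating will lose some discrimination. There will be more pregnancy reports and more infant follow-ups, each needing its own consent. The change should come early: revising Table 3 after years of ratings would leave the causality data on two scales.
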